As of November 22, 2015 (per the manufacturer's IB dated February 2016), data are available for 56 GSK sponsored clinical trials of AS03-adjuvanted monovalent pandemic vaccines manufactured by GSK. More than 18,000 adult (age ≥18 years) and 6,900 pediatric (6 months to 17 years old) clinical trial participants have received at least one dose of a GSK-manufactured, AS03-adjuvanted monovalent pandemic influenza vaccine. Clinical data collected by GSK as of November 22, 2015, suggest that inactivated monovalent (pre)pandemic influenza virus antigens adjuvanted with AS03 have generally acceptable safety and benefit/risk profiles, though the incidence rates of solicited local and systemic AEs are higher with AS03-adjuvanted antigens than with antigen alone, a licensed IIV3, or placebo. Some unsolicited AEs (e.g., insomnia, dizziness, cystitis) were associated with a higher relative risk among H5N1/AS03 recipients in contrast to Fluarix[®] or placebo recipients.

The information and guidance that follow are based on pre-clinical and clinical study results for GSK-manufactured AS03-adjuvanted monovalent pandemic vaccines, post-marketing safety surveillance data seen with unadjuvanted, IIV3s and (in the case of the H1N1 vaccines) post-marketing safety surveillance data seen to date for both PandemrixTM and ArepanrixTM H1N1 vaccines.

The reactogenicity profile in humans of GSK-manufactured AS03-adjuvanted vaccines is primarily associated with the adjuvant. The incidence and severity of injection site redness, swelling, and pain at the injection site in recipients of AS03-adjuvanted vaccines are increased relative to monovalent pandemic influenza antigen alone, a licensed IIV3, or placebo. There is no increase in injection site and systemic reactogenicity events in recipients of AS03-adjuvanted vaccines after a second dose of vaccine relative to the first when given 21 days apart. In young children (6 months to 6 years old), increased frequency of fever has been observed following a heterologous booster dose of adjuvanted vaccine administered 6 months after the primary series.

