- Presence of signs or symptoms that could confound or confuse assessment of study vaccine reactogenicity. For subjects with injection site or systemic signs or symptoms, or with an acute illness, including an oral temperature greater than or equal to 100°F, the second study vaccination should be postponed/deferred until signs, symptoms, or acute illness have resolved, or are improving as further specified below, and if within the acceptable protocol-specified window for that visit (Day 22+7).) No exceptions to the protocol-specified window will be made. Note for afebrile, acute illness only: If a subject is afebrile, his/her acute illness is nearly resolved with only minor residual symptoms remaining, this occurs within the acceptable protocol-specified window for that visit (Day 22+7), and, in the opinion of the site principal investigator or appropriate sub-investigator, the residual symptoms will not interfere with the ability to assess safety parameters as required by the protocol, the subject may receive the second study vaccination without further approval from the DMID Medical Officer. No exceptions to the protocol-specified window will be made. Grade 3 solicited or unsolicited AE that is ongoing, whether or not it is improved or resolving.
- Any unresolved or continuing Grade 2 AE that has not decreased in severity to Grade 1 or less.
- An unresolved or continuing Grade 1 AE is permissible following the documented determination by the site PI or appropriate sub-investigator, that it would not render study vaccination unsafe or interfere with the evaluation of responses.

- Grade 3 solicited or unsolicited AE that occurs without alternative etiology in the 8 days following the first study vaccination.
- of Grade 3 clinical safety laboratory value (according to the toxicity table, Section 9.2.3) that does not decrease to Grade 2 or less prior to the second study vaccination. Any clinical safety laboratory parameter may be re-evaluated only once at the central (clinical) laboratory in order to assess eligibility prior to the second study vaccination. If the clinical safety laboratory value decreases to Grade 2 or less, the subject may receive the second study vaccination. The second study vaccination should be scheduled to occur within the acceptable protocol-specified window for that visit (Day 22+7 days post first study vaccination). No exceptions to the protocol-specified window will be made.

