6.3.3. Per Protocol Population

The per protocol (PP) population includes all subjects in the mITT subset with the following exclusions:

- Data from all available visits for subjects found to be ineligible at baseline due to eligibility criteria that would impact immune response.
- Data from all visits subsequent to major protocol deviations, such as:
 - o Second study vaccination not received,
 - o Second study vaccination received out of window,
 - Receipt of non-study licensed live vaccine within 30 days before or after each study vaccination,
 - Receipt of non-study licensed inactivated vaccine within 14 days before or after each study vaccination,
 - Receipt of immunosuppressive therapy (e.g., corticosteroids) within 30 days before or after each study vaccination.
- Data from any visit that occurs out of window by more than one day:
 - O Visit 3 data collected before 6 days or after 10 days post first study vaccination
 - o Visit 4 data collected before 20 days or after 29 days post first study vaccination.
 - o Visit 6 data collected before 6 days or after 10 days post second study vaccination.
 - o For subjects who did not receive the second study vaccination, visit 6 data collected before 27 days or after 31 days post first study vaccination.
 - o Visit 7 data collected before 20 days or after 29 days post second study vaccination.
 - o For subjects who did not receive the second study vaccination, visit 7 data collected before 41 days or after 50 days post first study vaccination.
 - Visit 10 data collected before 165 days or after 195 days post second study vaccination.
 - o For subjects who did not receive the second study vaccination, visit 10 data collected before 200 days or after 216 days post first study vaccination.

For analyses using the PP population, subjects will be grouped based on study vaccinations received.

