8.1. Primary Immunogenicity Analysis

The primary immunogenicity endpoints HAI and Neut seroconversion, percentage of subjects with titer ≥1:40, and GMTs against the homologous A/H7N9 vaccine strain 21 days after the second vaccination will be summarized as described above. Regression modelling of seroconversion and log titers is planned as described in Section 8.3.2.

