8.3. Exploratory Immunogenicity Analyses

Immunogenicity data summaries and analysis for exploratory endpoints will be presented for the PP populations.

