8.3.2. Regression Modeling

Logistic and multivariate linear regression will be utilized to test for the effects of the HA antigen dose and the AS03 adjuvant on seroconversion and GMT, respectively, for the PP population. Similar models will be fit for HAI and Neut Antibodies. Separate models will be fit for data from Day 21 post dose 2 and Day 180 post dose 2.

Logistic regression will be fit to examine the relationship of HAI seroconversion at 21 days after the 2nd study vaccination with treatment group and age strata (19-64 years, ≥65 years). If the available titer data meets the required assumptions of normality after log transformation, multiple linear regression will be fit to examine the relationship of log transformed titers at 21 days after the 2nd study vaccination with treatment arm and age strata (19-64 years, ≥65 years). Both models will be fit with and without adjustment for the following covariates (*Z*): sex (female, male), BMI (<30, ≥30), and prior receipt of seasonal influenza vaccine (none in past 2 seasons, at least once in past 2 seasons). Modeling assumptions will be checked using standard diagnostic methods (e.g., using the INFLUENCE option in PROC LOGISTIC or PROC GLM). Parameter estimates and odds ratio estimates for the logistic models will be presented in Table 53, Table 54, Table 55, Table 56, Table 57, Table 58, Table 59, and Table 60. Parameter estimates for the multiple linear regression models will be presented in Table 61, Table 62, Table 63, Table 64, Table 65, Table 66, Table 67, and Table 68.

Model 1A: Logistic Regression (without covariate adjustment):

 $logit[P(seroconversion)] = \beta_0 + \beta_1 \times Treatment + \beta_2 (Age \ge 65) + \varepsilon$

Model 1B: Logistic Regression (with covariate adjustment):

$$logit[P(seroconversion)] = \beta_0 + \beta_1 \times Treatment + \beta_2 (Age \ge 65) + \beta_3 \times Z + \varepsilon$$

Model 2A: Multiple Linear Regression (without covariate adjustment):

$$log(titer) = \beta_0 + \beta_1 \times Treatment + \beta_2(Age \ge 65) + \varepsilon$$

Model 2B: Multiple Linear Regression (with covariate adjustment):

$$log(titer) = \beta_0 + \beta_1 \times Treatment + \beta_2(Age \ge 65) + \beta_3 \times Z + \varepsilon$$

Subjects missing data for one or more covariates will be excluded from Models 1B and 2B.

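### The between-arm models for antigen dose and AS03 are planned only in the per-protocol population, where exclusion may be related to treatment; as-randomised mITT fits should stand beside them

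*SAP*

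**What the plan says.** **Models.** SAP 8.3.2 uses logistic regression for seroconversion and linear regression for log titer "to test for the effects of the HA antigen dose and the AS03 adjuvant on seroconversion and GMT, respectively, for the PP population". Tables 53-70, which hold the results, are all titled Per Protocol, and their shells print p-values. The models sit under SAP 8.3, where "Immunogenicity data summaries and analysis for exploratory endpoints will be presented for the PP populations". SAP 8.1, on the primary endpoints, also relies on them: "Regression modelling of seroconversion and log titers is planned as described in Section 8.3.2".

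**Populations.** SAP 8 says that primary and secondary immunogenicity endpoints will be summarised and analysed in both mITT and PP. Protocol 11.6.3 says this of immunogenicity data generally. SAP 12 declares no change from the protocol's analyses. The mITT tables (29, 31, 33 and 35) give estimates and confidence intervals for each arm, without a contrast between arms. SAP 6.3.2 groups mITT subjects by randomised arm. For PP, "For analyses using the PP population, subjects will be grouped based on study vaccinations received".

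**PP exclusion.** SAP 6.3.3 removes visits after major deviations, the first example being "Second study vaccination not received". Tables 15 and 16 list this as a reason for exclusion from PP at Day 29 and Day 43. The same section also sets a PP window "For subjects who did not receive the second study vaccination, visit 7 data collected before 41 days or after 50 days post first study vaccination", with similar windows for visits 6 and 10.

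**Link to reactions.** Among the events for which protocol 5.2.3 withholds dose 2 is a "Grade 3 solicited or unsolicited AE that occurs without alternative etiology in the 8 days following the first study vaccination". An ongoing Grade 3 event, or a Grade 2 event that has not improved, also counts. Protocol 2.3.1 reports for the adjuvant manufacturer's AS03 vaccines that "the incidence rates of solicited local and systemic AEs are higher with AS03-adjuvanted antigens than with antigen alone", and that injection site redness, swelling and pain are also more severe. It adds that adverse events may be more frequent at higher antigen doses.

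**The concern.** Randomisation makes the arms comparable at enrolment. The PP models then condition on an event after dose 1, receipt of dose 2, which the assigned product may influence. If an AS03 arm loses more subjects this way than an unadjuvanted arm, or one antigen dose loses more than another, the modelled contrast no longer compares the randomised groups.

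These are the only planned between-arm estimates and p-values for immunogenicity. A reader of the clinical study report would have no as-randomised contrast against which to see whether exclusion mattered. The large AS03 contrast is little exposed. The smaller contrasts between adjuvanted dose arms, which bear on dose sparing, are more exposed if denial of dose 2 differs by antigen dose.

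**Working it through.** **Step 1: reproduce the plan's figures.** Protocol Table 6 (SAP Table 7) gives the lower 95% Farrington-Manning bound for adjuvanted (N = 100) minus unadjuvanted (N = 50), with an unadjuvanted rate of 0.10. A score interval with constrained maximum-likelihood variance gives, for adjuvanted rates of 0.50 to 0.90:

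- computed: 0.256, 0.356, 0.458, 0.563, 0.672
- stated: 0.26, 0.36, 0.46, 0.56, 0.67

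Protocol Table 7 (N = 50 and 25) also reproduces: 0.187, 0.286, 0.388, 0.493, 0.604 against 0.19, 0.29, 0.39, 0.49, 0.60.

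**Step 2: what is known about exclusion.** Protocol 11.4.2 expects PP exclusions of up to 5% at 19-64 years and 12% at 65 years and over. In total this is 400 × 0.05 + 240 × 0.12 = 48.8 of 640, or 7.6%. These rates cover every cause (no dose 2, loss to follow-up, other deviations) and are not split by arm. The share denied dose 2 for reactions is not given.

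**Step 3: as-randomised response, over an assumed range.** Let d be the share of an AS03 arm denied dose 2. Assume:

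- d = 2%, 5%, 7% or 12%. The 7% is the protocol 9.5 halting threshold for the same Grade 3 related reaction, and the 12% is the all-cause figure; both serve only to span a range.
- no denial in the unadjuvanted arm
- PP rates of 0.70 (AS03) and 0.10 (unadjuvanted)
- a response rate of 0.10 in denied subjects

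Rate with denied subjects kept in their arm = (1 − d) × 0.70 + d × 0.10. For d = 5%: 0.95 × 0.70 + 0.05 × 0.10 = 0.670. The difference is 0.570, against 0.60 in PP. The odds ratio is (0.670/0.330) ÷ (0.10/0.90) = 18.3, against 21.0.

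| d | AS03 rate | Difference | Shift | Odds ratio | Lower bound (100 vs 50) |
|---|---|---|---|---|---|
| PP | 0.700 | 0.600 | – | 21.0 | about 0.46 |
| 2% | 0.688 | 0.588 | 0.012 | 19.8 | 0.445 |
| 5% | 0.670 | 0.570 | 0.030 | 18.3 | 0.427 |
| 7% | 0.658 | 0.558 | 0.042 | 17.3 | 0.415 |
| 12% | 0.628 | 0.528 | 0.072 | 15.2 | 0.384 |

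**Step 4: a different target.** Suppose the target is the response if everyone had received two doses, the true rate is 0.70, and denied subjects would have responded at rate h. The PP rate is then (0.70 − d × h)/(1 − d). With d = 2% and h = 0.90 it is 0.696, or 0.4 points too low. With d = 12% and h = 1.00 it is (0.70 − 0.12)/0.88 = 0.659, or 4.1 points too low. The sign is now opposite to step 3.

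**Step 5: contrasts between adjuvanted arms.** By the step 3 formula, a 5-point difference in denial between two dose arms moves their contrast by 0.05 × (0.70 − 0.10) = 0.03. Protocol Table 5 puts the detectable difference at a comparator rate of 0.70 at 0.16 (N = 100) and 0.21 (N = 50). The shift is small beside these, but it would be invisible.

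**The case against.** **Limited consequence.** The trial disclaims formal hypothesis testing, and protocol 11.6.3 and SAP 8.3 class the models as exploratory. The mITT tables give n, percentages and GMTs by arm and age stratum, so a reader can compute an unadjusted as-randomised difference. The primary objective concerns response after two doses, which PP addresses directly. All of this stands. It makes the point a recommended addition rather than a defect in the primary summaries. It does not remove it, because SAP 8.1 attaches the models to the primary endpoints and the shells print p-values.

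**A stronger reading on direction.** A reader might infer that PP necessarily flatters AS03. The documents do not support that. Steps 3 and 4 give opposite signs for two reasonable targets, and no passage links reactions to antibody response. Nor is a Grade 3 rate given: the statements on AS03 concern solicited events overall and injection site severity.

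**A stronger reading on size.** A reader might apply the 5% and 12% directly, so that a PP rate of 80% becomes 0.95 × 0.80 = 76% or 0.88 × 0.80 = 70% of those randomised. This treats all-cause exclusions as reaction-related denials and counts every excluded subject as a non-responder. An mITT model would not return those figures. It needs a valid post-vaccination result, SAP 6.5 imputes nothing, and subjects lost before Day 43 contribute no Day 43 value.

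**The remedy is incomplete.** Under protocol 5.2.4, one-dose subjects are only encouraged to give blood about 21 and 180 days after their last vaccination. That puts the first sample near Day 22, not Day 43. Against this, protocol 8.2.6 expects some of them at Visit 07, where an antibody sample is listed, and SAP 6.3.3 sets a window for it. Some Day 43 data should exist; how much is unknown.

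**As-received grouping adds little.** Injections are given in clinic by assignment, so it differs from randomised grouping only after misadministration. This is correct; the exclusion is what matters.

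**Conclusion.** The point holds for the immunogenicity models. They are planned in PP only, PP loses Day 43 data after a missed dose 2, and a missed dose 2 may depend on treatment. The PP contrast can therefore differ from the as-randomised one. Relative to the as-randomised response it can favour the more reactogenic arms; relative to a hypothetical two-dose effect its direction is not fixed.

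The size is about 1-7 percentage points, which rests on the assumptions of step 3; the 2-12% range is not a figure from the documents. Even at 12% the lower bound stays at 0.384, so the AS03 conclusion does not reverse at the effect sizes the plan assumes.

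Two wider inferences should not be drawn. It is not true that no planned model keeps all vaccinated subjects: the solicited-event models in SAP 9.3.1 use the Safety population. Nor do one-dose subjects vanish from PP altogether: their Day 8 and Day 22 results precede the deviation and stay. For later visits SAP 6.3.3 is inconsistent. The Table 15 shell settles Day 43 in favour of exclusion, but it has no Day 202 block, so the Day 180 models are left unclear.

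**What to change.** 1. In SAP 8.3.2, also fit Models 1A, 1B, 2A and 2B at Day 43, for HAI and Neut, in the mITT population by randomised arm. Report them beside the PP models.
2. Report by arm the number of mITT subjects with no Day 43 titer, and the number who missed dose 2 with the reason. Without these counts a reader cannot judge how far the mITT fit restores the randomised comparison.
3. In SAP 6.3.3, reconcile the exclusion for a missed second vaccination with the PP visit windows for one-dose subjects, and state the rule for Day 202.

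No change to the criteria for giving dose 2 is proposed.

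The cost is a SAP edit and a rerun of existing code: four models by two assays, so eight more exploratory tables. The mITT fit will remain incomplete where Day 43 samples are missing.

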6.2.2. Preliminary Report and CSR

Clinical, safety, and reactogenicity data through approximately 180 days after the second study vaccination will represent the primary clinical database for this trial. Once the last subject completes the visit that occurs approximately 180 days after the last study vaccination, the primary clinical database will be cleaned, monitored, and locked, and all serum samples will be sent for HAI and Neut antibody assays. Unblinded analyses of safety, reactogenicity, and available immunogenicity data (HAI and Neut antibody assays through Day 202) are planned. A preliminary report may be prepared by the SDCC after the primary clinical database is locked and all HAI and Neut data through 180 days after the last study vaccination are received. Regardless of whether a preliminary report is prepared, a "topline" set of the immunogenicity tables will be provided to DMID on an expedited timeline following laboratory database lock. These analyses may be made available to the sponsor for planning subsequent trials and to the lead principal investigator for publication. These analyses will not be used to make any decisions concerning the conduct of this trial. As it is anticipated that subjects will remain in long term safety follow-up at the time of these analyses, blinded investigators and DMID medical monitors not involved in the analysis, publication, or clinical study report preparation will be responsible for assessing SAEs and MAAEs including PIMMCs and new onset chronic medical conditions until all subjects have completed the final follow-up visit. All analyses of data included in the preliminary report for early release will be considered the final analysis of these data, and also included in the final CSR.

Tables and figures to be included in the Preliminary Report are indicated with the symbol * in the title. Topline tables to be generated after laboratory database lock are indicated with the symbol ‡ in the title.

Analysis of exploratory immunogenicity endpoints may be performed and released as the data are available from the research laboratory. Any such analyses would be considered the final analysis for the endpoint and included in the CSR.

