Models 1B and 2B, defined above, will also be fit for HAI at Day 21 replacing the binary age strata variable with age in years (continuous). The models as shown below assume a linear relationship between age in years and both probability of seroconversion and GMT. The validity of this assumption will be assessed prior to analysis and, if the relationship between age and response is found to be non-linear, adjustments will be made to model parameters to

satisfy regression assumptions. The results of these models will be presented in Table 69 and Table 70.

Model 3: Logistic Regression (with covariate adjustment):

$$logit[P(seroconversion)] = \beta_0 + \beta_1 \times Treatment + \beta_2 (Age in Years) + \beta_3 \times Z + \varepsilon$$

Model 4: Multiple Linear Regression (with covariate adjustment):

$$log(titer) = \beta_0 + \beta_1 \times Treatment + \beta_2(Age\ in\ Years) + \beta_3 \times Z + \varepsilon$$

Subjects missing data for one or more covariates will be excluded from Models 3 and 4.

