9.3.1. Solicited Events and Symptoms

Systemic solicited adverse events were collected pre-vaccination, and systemic and local solicited adverse events were collected at-least 20 minutes post-vaccination and then daily for 7 days after each vaccination and graded on a scale of 0 (absent), 1 (mild), 2 (moderate) and 3 (severe). Systemic events include fever, feverishness, fatigue, malaise, myalgia, arthralgia, headache, and nausea. The grading scale for systemic events, including quantitative grading for fever, is included in Table 11. Local events include pruritus, ecchymosis, erythema, induration/swelling, pain, and tenderness. Ecchymosis, erythema, and induration are measured by both functional and measurement grading scales as defined in Table 10.

When calculating the incidence of solicited events, each subject will be counted once at the highest severity following the applicable vaccination, and any repetitions will be ignored. For summaries presented separately for each vaccination, the denominator for percentages will be the number of subjects who received the respective vaccination with non-missing data for the event summarized. For summaries over all vaccinations the denominator will be the number of subjects who received at least one vaccination with non-missing data for the event summarized.

The number and percentage of subjects reporting at least one solicited adverse event of any severity will be summarized for each solicited symptom, any systemic symptom, any local symptom, and any symptoms. For each event the denominator is the number of subjects who received the applicable vaccination with non-missing data for the specific event. The 95% CI calculated using Clopper-Pearson methodology from a binomial distribution (SAS Proc Freq with a binomial option) will be presented (Table 75, Table 76, Table 77, Table 78, Table 79, and Table 80). Logistic regression models will be fit to estimate the effect of treatment and age on the probability of reporting any local event or reporting any systemic event (Table 81 and Table 82). If statistically significant effects are observed in the model for local events or systemic events, then additional models will be fit for each individual event of that type.

$$logit[P(Event)] = \beta_0 + \beta_1 \times Treatment + \beta_2 (Age \ge 65) + \varepsilon,$$

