- Table 52: Summary of Neutralizing Antibody Against 2017 A/H7N9 by Treatment Arm, Age Stratum and Prior Seasonal Influenza Vaccination at 180 Days Post Second Vaccination, Per-Protocol Population*

Table 53: Logistic Regression Model to Evaluate the Relationship of HA Antigen Dose and AS03 Adjuvant with HAI Seroconversion Against 2017 A/H7N9 at 21 Days Post Second Study Vaccination, Per Protocol Population*

Model Parameter	Parameter Levels	Parameter Estimate	SE	p-value	Odds Ratio	95%CI
Treatment	3.75 mcg with AS03 Adjuvant (reference)	-	-	-	-	-
	7.5 mcg with AS03 Adjuvant	XXX.X	xxx.x	x.xxx	xx.x	xx.x-xx.x
	15 mcg with AS03 Adjuvant	xxx.x	xxx.x	x.xxx	xx.x	xx.x-xx.x
	15 mcg without AS03 Adjuvant	xxx.x	xxx.x	x.xxx	xx.x	xx.x-xx.x
	45 mcg without AS03 Adjuvant	xxx.x	xxx.x	x.xxx	xx.x	xx.x-xx.x
Age	19-64 years (reference)	-	-	-	-	-
	≥65 years	XXX.X	xxx.x	x.xxx	xx.x	xx.x-xx.x
Interaction: Age*Treatment	Age*3.75 mcg with AS03 Adjuvant	-	-	-	-	-
	Age*7.5 mcg with AS03 Adjuvant	XXX.X	xxx.x	x.xxx	xx.x	xx.x-xx.x
	Age*15 mcg with AS03 Adjuvant	XXX.X	xxx.x	x.xxx	xx.x	xx.x-xx.x
	Age*15 mcg without AS03 Adjuvant	XXX.X	xxx.x	x.xxx	xx.x	xx.x-xx.x
	Age*45 mcg without AS03 Adjuvant	XXX.X	xxx.x	X.XXX	xx.x	xx.x-xx.x
	Age*3.75 mcg with AS03 adjuvant	-	-	-	-	-

N = XX subjects with results available at 21 days post second vaccination in the per protocol population. XX subjects missing covariate data were excluded from this analysis.

P-value for Treatment = 0.XXX; P-value for Age = 0.XXX; P-value for interaction of Treatment and Age = 0.XXX.

- Table 54: Logistic Regression Model to Evaluate the Relationship of HA Antigen Dose and AS03 Adjuvant with Neut Seroconversion Against 2017 A/H7N9 at 21 Days Post Second Study Vaccination, Per Protocol Population*
- Table 55: Logistic Regression Model to Evaluate the Relationship of HA Antigen Dose and AS03 Adjuvant with HAI Seroconversion Against 2017 A/H7N9 at 180 Days Post Second Study Vaccination, Per Protocol Population*
- Table 56: Logistic Regression Model to Evaluate the Relationship of HA Antigen Dose and AS03 Adjuvant with Neut Seroconversion Against 2017 A/H7N9 at 180 Days Post Second Study Vaccination, Per Protocol Population*

Table 57: Logistic Regression Model to Evaluate the Relationship of HA Antigen Dose and AS03 Adjuvant with HAI Seroconversion Against 2017 A/H7N9 at 21 Days Post Second Study Vaccination, Adjusted for Baseline Covariates, Per Protocol Population*

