Table 80: Number and Percentage of Subjects Experiencing Solicited Events with 95% Confidence Intervals by Symptom, Treatment Arm and Age Stratum Post Study Vaccination 2 – Safety Population *

[Footnote update] N = Number of subjects in the Safety Population who received the second vaccination.

Table 81: Logistic Regression Model to Evaluate the Relationship of HA Antigen Dose, AS03 Adjuvant, and Age with Reporting Any Local Event Post Any Study Vaccination – Safety Population *

Model Parameter	Parameter Levels	Parameter Estimate	SE	p-value	Odds Ratio	95%CI
Intercept	-	xxx.x	xxx.x	x.xxx	-	-
Freatment	3.75 mcg with AS03 adjuvant (reference)	-	-	-	-	-
	7.5 mcg with AS03 adjuvant	xxx.x	xxx.x	x.xxx	xx.x	xx.x-xx.x
	15 mcg with AS03 adjuvant	XXX.X	xxx.x	x.xxx	XX.X	XX.X-XX.X
	15 mcg without AS03 adjuvant	XXX.X	xxx.x	x.xxx	xx.x	XX.X-XX.X
	45 mcg without AS03 adjuvant	xxx.x	xxx.x	x.xxx	xx.x	xx.x-xx.x
Age	19-64 years (reference)	-	-	-	-	-
	≥65 years	XXX.X	xxx.x	x.xxx	xx.x	XX.X-XX.X
Interaction (Age * Treatment)	≥65 years * 7.5 mcg with AS03 adjuvant	XXX.X	XXX.X	x.xxx	XX.X	xx.x-xx.x
	≥65 years * 15 mcg with AS03 adjuvant	XXX.X	xxx.x	x.xxx	XX.X	XX.X-XX.X
	≥65 years * 15 mcg without AS03 adjuvant	XXX.X	xxx.x	x.xxx	XX.X	XX.X-XX.X
	≥65 years * 45 mcg without AS03 adjuvant	XXX.X	XXX.X	x.xxx	XX.X	xx.x-xx.x

N = XX subjects in the safety population.

P-value for Treatment = 0.XXX; P-value for Age = 0.XXX; P-value for interaction of Treatment and Age = 0.XXX.

Table with similar format:

Table 82: Logistic Regression Model to Evaluate the Relationship of HA Antigen Dose, AS03 Adjuvant, and Age with Reporting Any Systemic Event Post Any Study Vaccination (N=X) – Safety Population *

Table 83: Number and Percentage of Subjects Experiencing Solicited Events by Symptom, Maximum Severity and Treatment Arm Post Any Study Vaccination – Safety Population *

		3.75	Group 1 mcg A/I + AS03 (N=X)	H7N9		Group 2 mcg A/H + AS03 (N=X)			Group 3 mcg A/H + AS03 (N=X)	7N9		Group 4 mcg A/H (N=X)			Group : mcg A/H (N=X)	17N9
Symptom	Severity	n	%	95% CI	n	%	95% CI	n	%	95% CI	n	%	95% CI	n	%	95% CI
Any Symptom	None	Х	XX	xx-xx	х	XX	xx-xx	X	XX	xx-xx	х	XX	xx-xx	X	XX	xx-xx
	Mild	х	XX	xx-xx	X	XX	xx-xx	X	XX	xx-xx	X	XX	xx-xx	X	XX	xx-xx
	Moderate	х	xx	xx-xx	X	XX	xx-xx	X	xx	xx-xx	Х	xx	xx-xx	Х	XX	xx-xx
	Severe	х	xx	xx-xx	X	XX	xx-xx	X	xx	xx-xx	Х	xx	xx-xx	Х	XX	xx-xx
Any Systemic Symptom	None	Х	xx	xx-xx	Х	xx	xx-xx	X	xx	xx-xx	х	XX	XX-XX	Х	XX	xx-xx
	Mild	X	XX	xx-xx	X	XX	xx-xx	X	XX	xx-xx	X	XX	xx-xx	X	XX	xx-xx

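### SAP 8.3.2 and 9.3.1 specify additive treatment-plus-age models, but the table shells for them report an age-by-treatment interaction, so the Treatment rows have two possible meanings

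*SAP*

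**What the plan says.** SAP 8.3.2 sets out Models 1A, 1B, 2A and 2B for seroconversion and log titer, to examine the "relationship of HAI seroconversion at 21 days after the 2nd study vaccination with treatment group and age strata (19-64 years, ≥65 years"). Each equation is an intercept, Treatment and an indicator for age 65 or over; the B versions add covariates Z, defined as sex, BMI and prior seasonal vaccination. Models 3 and 4 are 1B and 2B refitted after "replacing the binary age strata variable with age in years (continuous"). SAP 9.3.1 gives the solicited-event model the same Treatment-plus-Age form. No equation has a product term. Neither these sections nor protocol 11.6.3 mentions an interaction.

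The shells differ. Tables 53, 57, 61, 65, 69 and 70 each have a block labelled "Interaction: Age*Treatment" and a footnote containing "P-value for interaction of Treatment and Age = 0.XXX". Table 81 has a block labelled "Interaction (Age * Treatment") and the same footnote. The reference levels are 3.75 mcg + AS03 and, where age is binary, 19-64 years. Table 82 is marked as having the format of Table 81. Tables 54-56, 58-60, 62-64 and 66-68 are listed under their parent shells with no layout of their own.

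Three other statements bear on the consequences:

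- SAP 8.1, on the primary immunogenicity endpoints: "Regression modelling of seroconversion and log titers is planned as described in Section 8.3.2".
- SAP 6.2.2: "All analyses of data included in the preliminary report for early release will be considered the final analysis of these data". Tables 53-70 and 81-82 carry the asterisk that assigns them to that report.
- SAP 9.3.1: "If statistically significant effects are observed in the model for local events or systemic events, then additional models will be fit" for each individual event.

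**The concern.** The two specifications are different models, and the row labels do not reveal which was fitted. With the shells' reference coding, adding the product terms changes what the Treatment rows estimate:

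- **Tables 53-68 and 81-82 (binary age).** The row goes from a common age-adjusted effect to the effect in 19-64 only. On the log-odds or log-titer scale, the effect in those 65 and over is then the sum of two rows, and no confidence interval is provided for it.
- **Tables 69-70 (age in years, no centring stated).** The row becomes the treatment effect at age 0, in a trial that enrols from age 19.
- **9.3.1.** The equation yields two overall tests (treatment, age) and the shell three. The text does not say which one counts as significant for starting the individual-event models.

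As the SAP stands, either fit departs from part of it. If the choice is left until the data are unblinded, it is an analyst's choice rather than a pre-specified one.

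**Working it through.** The contradiction rests on the text alone; there is no figure in the plan to reproduce. The calculations below only show how far apart the two versions can be.

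**1. Size of the models.** Before covariates, the additive model has 1 intercept + 4 treatment terms + 1 age term = 6 parameters. The shell has 6 + 4 product terms = 10.

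**2. Inputs for the illustration.**
- Evaluable numbers, from SAP section 5 and protocol 11.4.2: 100/100/100/50/50 in 19-64 and 50/50/50/25/25 in 65 and over.
- Unadjuvanted response rate 0.10, from SAP section 5.
- Assumed here: 19-64 rates of 0.60 for 3.75 mcg + AS03 and 0.75 for 15 mcg + AS03, with 7.5 mcg + AS03 varied over 0.60-0.75; a flat 0.50 in all adjuvanted arms at 65 and over. These lie within the SAP's 0.50-0.90 adjuvanted range, but the documents give no rates by dose and age.

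Both logistic models were fitted to the expected counts.

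**3. The 15 mcg + AS03 row when the dose effect differs by age.**
- Shell model, 19-64: OR = (0.75/0.25)/(0.60/0.40) = 2.00. SE of log OR = √(1/60 + 1/40 + 1/75 + 1/25) = 0.308. 95% CI 1.09-3.66, p = 0.0245.
- Shell model, 65 and over: OR = 1.00, SE = √(4 × 1/25) = 0.400, 95% CI 0.46-2.19. This is not printed under either version.
- Additive model: OR 1.54-1.55, SE 0.241-0.243, 95% CI about 0.96-2.5, p 0.071-0.073.

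**4. The same row when there is no interaction (0.60 to 0.75 in both strata).** The OR is 2.00 throughout, and only the precision changes:

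| Estimate | SE of log OR | Ratio to additive |
|---|---|---|
| Additive | √(1/90 + 1/60 + 1/112.5 + 1/37.5) = 0.252 | 1 |
| 19-64 | 0.308 | 1.22 |
| 65 and over | √(1/30 + 1/20 + 1/37.5 + 1/12.5) = 0.436 | 1.73 |

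The ratios equal √(150/100) and √(150/50), so they follow from the stratum sizes and not from the assumed rates.

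**5. Table 69 (age in years).** Ages are assumed evenly spread over 19-64 and 65-85, with OR 2.00 at every age. Under Model 3 the SE is 0.252 and the CI 1.22-3.28. Under the shell with uncentred age the SE is 0.729 (2.9 times larger) and the CI 0.48-8.34. Centring at the mean age of 52.7 brings the SE back to 0.252.

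**6. Cells with no responders.** At a 10% unadjuvanted rate, the chance that at least one of the four unadjuvanted arm-by-stratum cells is empty is 1 − (1 − 0.9^50)²(1 − 0.9^25)² = 0.147. For a whole unadjuvanted arm, which is what matters in the additive model, it is 1 − (1 − 0.9^75)² = 0.0007.

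**The case against.** The case on the other side concerns weight, not fact.

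- **The mismatch would be noticed.** An additive fit cannot fill the interaction rows or footnote, and SAP section 1 requires deviations to be justified in the clinical study report. This makes a silent error unlikely. It does not say which model is the planned one, and the SAP gives shells no priority over its text.
- **The stakes are low.** The immunogenicity models are exploratory, the trial tests no specific null hypothesis, and Tables 33-36 give the primary endpoints by arm and stratum whichever model is fitted. This stands. So does the point that 6.2.2 makes the Preliminary Report optional, although SAP 6.6 says a report through Day 43 will be prepared.
- **The change in significance depends on the chosen rates.** This is correct. With the 19-64 rate for 15 mcg + AS03 at 0.70 and 7.5 mcg at the midpoint, neither p-value is below 0.05 (0.24 additive, 0.14 shell). At 0.80 both are (0.015 and 0.002). With a dose effect that is steeper in those 65 and over, the shift reverses: OR 3.53 additive against 2.67 from the shell, at 100/60 and 50/30 per arm. Step 3 is therefore one scenario, not an expected size.
- **The 9.3.1 trigger is already vague** with two tests. True; the shell adds a third.
- **The empty-cell figure uses the minimum evaluable numbers.** With 30 rather than 25 per unadjuvanted arm at 65 and over, it falls from 15% to about 9%. A penalised fallback is a separate, optional matter.

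**Conclusion.** The concern holds. The SAP states two different models for the same tables, and nothing in the SAP or protocol reconciles them. The dependable measures of size are structural: four extra parameters, standard errors 1.22 times (19-64) and 1.73 times (65 and over) the additive one, and a Treatment row evaluated at age 0 in Tables 69-70. How far the odds ratios and p-values move depends on unknown response rates. The shift from OR 1.54-1.55 to 2.00 shows what is possible under the stated assumptions. The 2.9-fold figure for Table 69 also depends on the assumed age spread. Because the models are exploratory and the descriptive stratum tables do not change, this should be fixed before unblinding but does not threaten the trial's primary estimates.

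**What to change.** Specify one model in both the text and the shells before unblinding.

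- **Preferred.** Add Treatment × Age to Models 1A-2B and to the 9.3.1 model, because the immunogenicity objectives are stratified by age and the shells already carry the term. Replace the raw coefficient rows with treatment contrasts for 19-64 and for 65 and over, each with a 95% CI.
- **Acceptable alternative.** Delete the interaction rows and p-value from the shells. This also removes the contradiction, but imposes one treatment effect on both strata.
- **Models 3 and 4.** Drop the interaction rows from Tables 69-70, or centre age and report contrasts at stated ages.
- **9.3.1.** State which p-value triggers the individual-event models.
- **Optional.** Name a fallback, such as Firth penalised likelihood, for logistic fits with an empty responder cell.

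The cost is edits to equations and shell rows; no new data are needed. With the interaction, the stratum-specific intervals are wider on the log scale than a pooled effect, by about 22% in 19-64 and 73% in 65 and over.
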